PRIME Care (PRecision medicine In MEntal health Care)
Statistical Analysis Plan

Derived 7/2020 with the publication of the Methods paper ([name] et al 2021)
Reviewed and finalized prior to Analysis by Executive Committee on 8/16/21

The following statistical analysis plan was specified in the methods paper submitted in July 2020 for publication [34]). The methods paper was an expansion of the original grant application, which had limited specificity in the approach to analysis. In the paper, the original hypotheses were unaltered from the grant application, although edited for clarity. Prior to the conclusion of the study and prior to initiation of analyses, the Statistical Analytic Plan was reviewed by the Executive Committee and approved as amended below. We highlight only substantive changes from the methods paper as noted.

The primary hypotheses to be tested in the clinical trial component are that:

- 1) During the first six months of treatment, Veterans with MDD whose care is guided by the results of the PGx battery (the intervention group) will have a higher rate of remission of depression than the delayed results group. Remission is defined as a Patient Health Questionnaire (PHQ-9) score of 5 or less.
- 2) Over the first 30 days after randomization, provider/patient dyads in the intervention group will use fewer antidepressant medications that have potential gene-drug interactions based on commercial PGx test results than dyads in the delayed results group.

Rationale for amendments made– Neither the grant nor the methods paper specified the time frame of Hypothesis #2. This was discussed and approved by the Executive Committee on 8/16/21, and 30 days was agreed upon to evaluate the time most proximal to receiving the PGx results. A secondary outcome will evaluate the proportion of days on which patients were prescribed antidepressants with a significant drug-gene interaction over the 24 weeks with the expectation of small changes in prescribing over time.

The secondary hypotheses are that:

- 3) Veterans in the intervention group will have better secondary outcomes than the delayed results group over the 24 weeks post-randomization, including rates of depression symptom response (as indicated by a 50% reduction in PHQ-9 score from baseline) and changes in PHQ-9 score.
 - Other secondary outcomes will include side effect rates, treatment adherence rate, and functional improvement.

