- 4) In the delayed results group, there will be a decrease in the probabilities of antidepressants characterized as red or yellow prescribed in the 30 days after the release of the PGx test results, compared to the 30 days prior to release of results.

Rationale for amendments made– To clarify the intent of Hypothesis #4, it was agreed that this analysis would not be included in the primary paper.

Sample Size and Power Considerations.

We have two primary hypotheses, so we will test each at a 2.5% significance level, using two-sided tests.

The primary outcome for Hypothesis #1 is a set of repeated binary indicators of remission from depression. We assume a 20% loss to followup, distributed evenly over time, and across the two groups. The anticipated remission rate in usual care is based on results from STAR*D [2]. For the base rate, we consider rates of 20-25-30-35%, and for the treatment effect, we look at effects of about 5%. To account for correlations between the results for two patients of the same provider, we assume an intra-class correlation (ICC) of 0.05 or lower for providers, which should also address the nesting within sites [21]. We assume our design will have approximately 200 providers, with an average of ten patients per provider, so the design effect for an ICC of 0.05 is 1.45. For a base rate of 30% (based on results from STAR*D [2]), and an assumed within-patient correlation of 0.4 or lower in a compound symmetry structure, we have 82% power for a 5% treatment effect and 92% power for the same effect in an autoregressive (ar(1)) structure, with higher power for the same 5% effect with lower base rates. For a provider ICC of 0.01, where we have an effective sample size of 1835, we have power in excess of 90% for 5% effects, under either covariance structure.

For Hypothesis #2, the primary outcome is an ordinal response indicating the gene-drug interaction potential (coded as green, yellow, and red based on the PGx test for non, moderate and significant drug- gene interactions) of the initial prescription made during the intervention period. Assuming that the overall proportions in the sample are approximately 40%/40%/20% for green/yellow/red, respectively, then our sample of 2000 provides 80% power to detect a common odds ratio of 1.29 under a proportional odds model, at a significance level of 2.5%.

Data Analysis Plan for the Completed Sample.

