Prior to performing analyses, we will apply standard data-cleaning procedures. Specifically, we (1) screen the data for data-entry errors, (2) check for outliers, (3) assess the extent and pattern of missing data, and (4) check that appropriate assumptions of normality for data distributions are met whenever necessary.

Primary hypotheses.

Patient response to treatment (Hypothesis #1). The primary outcome measures will be a set of binary indicators of remission (PHQ-9 score ≤ 5) across the intervention phase time points (weeks 4, 8, 12, 18, and 24). We will use a mixed-effects logistic regression model to test the hypothesis that patients whose treatment is informed by the PGx results are more likely to be in remission than those receiving usual care. The model will have a binary indicator of intervention group as the main explanatory variable, together with the baseline phq-9 score, and variables for time and group-by-time effects, and a fixed effect for site. To accommodate nesting of repeated measures within patients, and nesting of patients within providers, the models will include a random intercept for provider and correlated residuals within patient; we will use information-criteria comparisons to compare the fit of different covariance structures to ensure adequate fit. As there is particular interest in the remission rate of patients at the end of treatment, we will report on a comparison between the groups at the endpoint of the intervention phase (week 24), based on our final model.

Patient and provider use of PGx results (Hypothesis #2). For each provider-patient dyad in the trial, we will use the results of the PGx battery to classify each antidepressant medication prescribed by the provider to that patient during the study period as green, yellow, or red, thus creating an ordinal measure for each time the provider prescribes a medication. The primary outcome for Hypothesis #2 will be the ordinal variable corresponding to prescriptions written in the first 30 days after randomization. In the case of Veterans having simultaneous prescriptions, we will use a “worst-case” approach, assigning the highest level of the green, yellow and red scale. We will compare the groups on their probabilities of prescriptions of green, yellow, or red using a mixed-effects ordinal regression model, including random intercepts for providers and fixed effects for sites.

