Dropout and Missing Data. We anticipate that there will be dropout from the study as well as intermittent missing data, in particular for the patient outcome responses of Hypothesis #1, while some Veterans may not receive an antidepressant prescription in the 30-days post-randomization for Hypothesis #2. The mixed-effects models described above for Hypothesis #1 make use of all available responses, can accommodate the heterogeneity of response times caused by intermittent missing data, and provides valid estimates and hypothesis tests under an assumption of ignorable missingness. To assess the sensitivity of our conclusions to this assumption, we will extend the mixed-effects models to consider inverse probability-weighted selection models and pattern mixture models [22]. We will perform these analyses under a range of different prediction models and assess the sensitivity of the results. For Hypothesis #2 we will use a multiple imputation approach. [32-33]

Secondary Hypotheses.

Secondary Responses (Hypothesis #3). We will compare the intervention groups on their repeated depression response outcomes using mixed effects logistic regression models, as described for primary Hypothesis #1. For the PHQ-9 summary score of depression severity, we will use mixed-effects linear models.

We will use generalized linear regression models to compare the groups on side effect rate, treatment adherence rate, and functional improvement. Regression models will include random effects to accommodate correlations due to nesting of patients within providers, and repeated measures (where necessary).

Rationale for amendments made– Number of outpatient visits was removed from the secondary outcomes as there are no standards for an acceptable frequency of outpatient visits, particularly when comparing specialty mental health care and primary care.

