We will also compare the groups on the rates of side effects that are moderate or severe. Side effects may be more plausibly related to serum antidepressant levels and thus PGx results than depressive symptoms. The data will include binary ratings of presence of moderate to severe headache, nausea or vomiting, diarrhea, constipation, and sexual dysfunction at weeks 4, 8, 12, 18, and 24. We will use a mixed-effects logistic regression model to test whether there are differences in the probabilities of moderate or severe side effects between the two intervention groups. We will compare the groups on functional improvement, using the mental health component of the VR-12 score, with analogous generalized linear mixed-effects models appropriate to the response distribution.

We will compare differential outcomes by randomized group on adherence rates. For Hypothesis #1, there are two types of adherence to be considered. First, a provider/patient dyad in the intervention group may not use a recommended medication (this is the focus of Hypothesis #2 with the analytic plan described above). The second form of adherence is whether the patient is actually taking their medication as prescribed. We assess medication adherence using electronic health record data on prescriptions filled. From the prescriptions filled data, we will calculate an antidepressant medication possession ratio. For each Veteran, we will create a binary variable, indicating whether they filled medication prescriptions for at least 80% of days through the 24-weeks treatment period, and compare the groups on this outcome using logistic regression models, as described above.

Rationale for amendments made– The above section on adherence was amended from the methods paper to separate the analysis for Hypothesis #2 and to further clarify medication adherence as a secondary outcome. Originally proposed was a self-reported variable on adherence. However, during the trial it was apparent that the validity of this assessment was suspect as patients often didn't remember their medications and had difficulty assessing adherence to specific medications. Prescription fill rates is considered a more reliable method for ascertaining availability of medication though it does not assess whether the patient has taken the medication. Below we also clarify that the proposed adherence by treatment interaction analysis was to be explored in secondary manuscripts.

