In secondary manuscripts, we will assess the sensitivity of the results of the analyses described above to non-adherence, by extending the models described above for primary and secondary outcomes using instrumental variable approaches. Here, the instrumental variable is randomization that, under some conditions, will control for unmeasured bias (due to self-selection to adhere or not) when estimating the relative effects of the medications in those who adhere to their assigned medication. Results will use data from all patients who show various degrees of adherence as measured by the availability of medication or adherence to the PGx recommendation and will yield estimates of the intervention effects that would have been seen in a study with full adherence. For a single overall measure of adherence, we will use the methods of Nagelkerke et al. [25]; if there is sufficient within-patient variation across time in adherence, we will use the longitudinal methods of Small et al. [26].

Change in prescribing in delayed results group post-intervention (Hypothesis #4). At the conclusion of the six-month intervention phase of the trial, the PGx battery results are returned to the providers (and patients) in the delayed group. The primary outcome for Hypothesis #4 will be the ordinal variable corresponding to prescriptions written in the first 30 days after return of results. We will use a mixed-effects ordinal regression model to test whether the probabilities of red and yellow medications decrease from before the release of the PGx results through the 30 days after release.

Further descriptive analyses:

Rationale for amendments made– Not specified in the methods paper are descriptions of the impact of the study on routine clinical care. To describe potential delays in care associated with the time of collecting and releasing PGx results, we will present data on the time from randomization to the release of the PGx results in the intervention arm. Descriptive data of participating providers and randomized participants will also be provided in the primary outcomes.

References:

2. Trivedi, M.H., et al., *Evaluation of outcomes with citalopram for depression using measurement-based care in STAR*D: implications for clinical practice*. Am J Psychiatry, 2006. **163**(1): p. 28-40.

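### Hypothesis #4 gives no score to a delayed-arm patient who continues on existing supply, and this can overstate a real fall in red or yellow antidepressants after the results are released

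*SAP*

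**What the plan says.** The SAP's list of secondary hypotheses words Hypothesis #4 as a lower probability of red or yellow antidepressants "prescribed in the 30 days after the release of the PGx test results, compared to the 30 days prior to release of results". The section on change in prescribing in the delayed group then defines the measure: "The primary outcome for Hypothesis #4 will be the ordinal variable corresponding to prescriptions written in the first 30 days after return of results". A mixed-effects ordinal model is to "test whether the probabilities of red and yellow medications decrease from before the release of the PGx results through the 30 days after release".

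The colour measure comes from Hypothesis #2, where the SAP creates one score per act of prescribing. The scale is green, yellow, red. It has no level for nothing written and no carry-forward for a drug still in supply. The only tie rule is for simultaneous prescriptions, "assigning the highest level of the green, yellow and red scale".

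Under Dropout and Missing Data the SAP recognises the empty window, but for one hypothesis only: "some Veterans may not receive an antidepressant prescription in the 30-days post-randomization for Hypothesis #2". The remedy is equally restricted: "For Hypothesis #2 we will use a multiple imputation approach". Nothing is said for Hypothesis #4.

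Two other measures look at drug exposure over time. One is "A secondary outcome will evaluate the proportion of days on which patients were prescribed antidepressants with a significant drug-gene interaction over the 24 weeks". The other is the adherence measure: "From the prescriptions filled data, we will calculate an antidepressant medication possession ratio". Both stop at week 24, when the delayed arm receives its results. Protocol section 5.6.d words Hypothesis #4 in terms of medications received, with no 30-day window.

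**The concern.** The 30-day window suits Hypothesis #2. Every patient enters intending to start an antidepressant (Protocol 5.4), and the coordinator checks the chart for a prescription between randomisation and the one-month blood draw and queries the provider if there is neither a prescription nor a note explaining its absence (Protocol 6.0). The documents describe no such trigger or check when results are released to the delayed arm. By then a patient may simply be continuing treatment.

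Take two patients on a red drug at release. One is switched to green: a prescription is written and the patient is scored green. The other is left unchanged on existing supply: nothing is written and the patient has no score. Being observed after release therefore depends on the outcome itself. A model that uses all available responses under ignorable missingness need not correct that.

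What is at stake is how far prescribers act on the report. A provider who reads it and changes nothing may leave no trace in the analysis, while one who switches always does.

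**Working it through.** **No figure to reproduce.** The documents give no sample size, power, significance level or effect for Hypothesis #4. The only stated power on this colour scale is for Hypothesis #2. As a check on the borrowed colour split, Whitehead's formula with 40/40/20, odds ratio 1.29, 80% power and two-sided 2.5% gives N = 12(2.241 + 0.842)² / [(ln 1.29)² × (1 − 0.136)] ≈ 2036, close to the SAP's 2000.

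**Inputs**
- p = 0.60, the share on red or yellow before release. This is 40% + 20% from the SAP's Hypothesis #2 power text, borrowed here; it is not a figure for the delayed arm at week 24.
- s = 0.10, the share of red or yellow patients switched to green within 30 days of release. Assumed.
- f, the share of unchanged patients with a prescription written in a 30-day window, equal for all colours and both windows. Assumed; varied from 1/5 to 1.
- Every switch generates a written prescription, and refills do not count as written. Assumed; the SAP does not say whether refills count.

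**Formulas**
- True fall = p·s = 0.60 × 0.10 = 6.0 points (60% to 54%).
- Red or yellow share among scored patients before release = p, because f cancels.
- After release = f(1−s)p / [f(1−s)p + s·p + f(1−p)] = 0.54f / (0.54f + 0.06 + 0.40f).

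| f | Scored share after release | Apparent fall (points) | Ratio to true fall |
|---|---|---|---|
| 1 | 0.540 / 1.000 = 54.0% | 6.0 | 1.00 |
| 2/3 | 0.360 / 0.687 = 52.4% | 7.6 | 1.26 |
| 1/2 | 0.270 / 0.530 = 50.9% | 9.1 | 1.51 |
| 1/3 | 0.180 / 0.373 = 48.2% | 11.8 | 1.96 |
| 1/5 | 0.108 / 0.248 = 43.5% | 16.5 | 2.74 |

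At s = 0.20 the true fall is 12.0 points and the apparent fall is 14.7, 17.1, 21.3 and 27.6 points for f = 2/3, 1/2, 1/3 and 1/5. Over p from 0.4 to 0.7, s from 0.05 to 0.30 and f from 1/5 to 2/3, the ratio runs from 1.13 to 3.33.

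**Who is lost.** At f = 1/3 and s = 0.10, the red or yellow stayers without a score are 0.54 × 2/3 = 36% of the arm, or about 360 of an assumed 1000. Green patients on existing supply also drop out, and both windows lose patients.

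**When the effect vanishes or reverses**
- s = 0: the scored share is p in both windows, so the fall is zero at every f.
- Unequal renewal after release: let green stayers stay at 1/3 and red or yellow stayers be re-prescribed at g. The apparent share equals the true 54% when 0.54g / (0.54g + 0.06 + 0.133) = 0.54, that is g = 0.193 / 0.46 ≈ 42%. Above that, the fall is understated. At s = 0.20 the threshold is about 49%.
- If a patient with nothing written were counted as not red or yellow, f = 1/3 gives 20% to 18%. The absolute fall is then 2 points, not 6, with the relative fall unchanged.

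**The case against.** The strongest reply is that Hypothesis #4 is about prescribing behaviour. The section is headed as a change in prescribing, and the colour mix of new prescribing decisions is a legitimate measure of it. On that view nothing is overstated; the measure merely differs from drug in hand. This stands in part, and is a reason to keep the written-prescription measure as a description. It does not supply a value for the provider who decides to leave the drug alone, which is also a prescribing decision. The protocol's wording is about medications received.

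The second reply is that the direction is not certain, and this stands. Protocol 5.2 says results inform both the drug and the target dose. A provider who responds by changing the dose of a red or yellow drug may write a red or yellow prescription, which raises re-prescribing among stayers. A gap of about 42% against 33% is enough to remove the bias in the example.

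The third reply is that the size comes from chosen inputs. This also stands: the documents give no supply length, refill practice or switch rate. A reader might infer that most of the delayed arm is discarded, or that the fall is inflated two to four times. Neither follows. At renewal rates of 1/2 and 2/3 the inflation in the main example is 1.5 and 1.3 times. Nor is it true that the bias disappears only when every patient has a prescription in each window, as the 42% case shows.

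**Conclusion.** The point holds as a flaw in how the outcome is defined, with a conditional bias. It is certain from the text that the outcome rests on prescriptions written in two 30-day windows, that a patient continuing on existing supply has no defined value, and that no missing-data rule covers Hypothesis #4. Selection on the outcome follows if continuing patients need no newly written prescription.

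Overstatement of a real fall follows if refills do not count as written and unchanged patients of all colours renew at similar rates below 100%. Under those conditions a true 6-point fall appears as roughly 7.6 to 16.5 points for renewal rates from 2/3 down to 1/5, given the borrowed 60% and an assumed 10% switch rate. A reader might infer that the fall will be overstated outright, or that a fall could appear where none exists. The documents do not settle the conditions for the first. The second does not arise from this mechanism when there is no switching and renewal rates are equal.

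The consequence is limited: Hypothesis #4 is secondary and will not be in the primary paper. The rule is still worth changing, because as written it can mislead about uptake of the report.

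**What to change.** Define the Hypothesis #4 outcome as the colour of the patient's current antidepressant (active prescription, or days' supply from VA pharmacy records) on the day before release and on day 30 after release, for every delayed-arm patient with an active antidepressant. In the example this returns the true 6.0 points whatever the renewal rate.

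The wording should also:
- score the newly started drug where a switch has occurred, so that leftover supply of the replaced drug does not trigger the worst-case rule and hide the switch; keep that rule for drugs prescribed concurrently;
- state whether refills count;
- report the number with no active antidepressant at each date;
- keep prescriptions written as a descriptive measure of provider action, with the number of patients scored in each window.

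The cost is SAP wording plus some data work. Fills after week 24 must be extracted, since neither the possession ratio nor the 24-week days outcome reaches them, and days' supply must be mapped to dates. The extraction is within scope: Protocol 5.5 (the electronic health record and CDW items) provides for pharmacy records up to 12 months after the study period.
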